8.2. PK Parameter Analysis

All individual PK parameter calculations will be performed using actual time points calculated relative to the time of starting administration of Advate or BIVV001.

Individual PK parameter estimates will be listed for each subject and summarized descriptively by drug and dose level group for both FVIII activity assays. Summary descriptive statistics will include the number of observations, arithmetic and geometric means, standard deviation, coefficient of variation, minimum, and maximum.

An analysis of variance model with factors for drug and subject will be used to compare BIVV001 to Advate for the analysis of selected PK parameters, including but not limited to C_{max} , $t_{1/2}$, CL, V_{ss} , AUC_{∞} , MRT, IR, and time to 1% above baseline for FVIII activity. Analyses will be performed for each dose level separately. PK parameters will be log-transformed for these analyses, and estimated means, mean differences, and CIs on the log scale will be exponentiated to obtain estimates for geometric means, geometric mean ratios, and CIs, respectively, on the original scale.

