3. STUDY DESIGN

3.1. Overall Study Design

[figure not shown]
This is a Phase 1/2a, open-label, dose-escalation, multicenter study designed to evaluate the safety, tolerability, and PK of a single IV dose of BIVV001 in subjects with severe hemophilia A who have received at least 150 exposure days of prior FVIII treatment.

Approximately 18 male PTPs aged 18 to 65 years will be enrolled: approximately 8 subjects in the low-dose cohort (Advate 25 IU/kg and BIVV001 25 IU/kg) and approximately 10 subjects in a high-dose cohort (Advate 65 IU/kg and BIVV001 65 IU/kg).

Each subject will be dosed with Advate followed by a PK sampling period. Following a brief washout period, each subject will then be administered BIVV001 followed by a PK sampling period. Subjects will undergo safety observation for 28 days following the injection of BIVV001, including sample collection for inhibitor assessments 14 and 28 days after the injection of BIVV001. Subjects may resume treatment with their pre-study FVIII product during the 28-day observation period after completing Visit 14 activities (which include the 14-day inhibitor test). Only subjects with adequate samples for PK and inhibitor characterization following both Advate and BIVV001 dosing will be considered evaluable; additional subjects will be enrolled as needed to ensure that at least 6 subjects in the low-dose cohort and 8 subjects in the high-dose cohort provide evaluable PK and inhibitor data.

An independent Data Safety Monitoring Committee (DSMC) will evaluate the safety data from the study on an ongoing basis.

Figure 1: Study Schema

* Screening may be extended up to 120 days with prior Sponsor approval. If the Screening Period extends beyond 56 days, screening assessments must be repeated as specified in the protocol prior to dosing with Advate. Washout duration at least 96 hours (4 days) from the most recent FVIII dose (prestudy FVIII) for a conventional product, 120 hours (5 days) for an extended half-life FVIII product.

[figure not shown]
** Washout duration at least 72 hours (3 days) from the Advate dose for the BIVV001 low-dose cohort, and at least 96 hours (4 days) for the BIVV001 high-dose cohort.

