3.2. Statistical Hypothesis

No formal statistical hypothesis will be tested.

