3.3. Sample Size Considerations

The sample size for this study is based on the need to establish the initial safety profile of BIVV001 and characterize its PK profile. The number of subjects who have severe hemophilia A is small; thus, the determination of sample size for this study is constrained by subject availability. Approximately 18 subjects will be enrolled and treated. Additional subjects may be enrolled to ensure that at least 6 subjects from the low-dose cohort and 8 subjects from the high-dose cohort provide evaluable PK and inhibitor data.

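### If subject is a fixed factor in the Section 8.2 ANOVA, the confidence interval for each drug's geometric mean leaves out between-subject variance and is too narrow; the ratio interval is sound

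*SAP*

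**What the plan says.** Section 8.2 specifies the comparison model: "An analysis of variance model with factors for drug and subject will be used to compare BIVV001 to Advate". The parameters are log-transformed, and "Analyses will be performed for each dose level separately". The outputs are named next: "estimated means, mean differences, and CIs on the log scale will be exponentiated to obtain estimates for geometric means, geometric mean ratios, and CIs", matched item by item and on the original scale. Neither this section nor any other part of the SAP mentions a random effect or a mixed model. The SAP also gives no confidence level.

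The data are paired. Each subject receives Advate first, and then: "Following a brief washout period, each subject will then be administered BIVV001 followed by a PK sampling period". The planned size is "approximately 8 subjects in the low-dose cohort (Advate 25 IU/kg and BIVV001 25 IU/kg) and approximately 10 subjects in a high-dose cohort" (Section 3.1), and Section 3.3 asks that "at least 6 subjects from the low-dose cohort and 8 subjects from the high-dose cohort provide evaluable PK and inhibitor data".

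Section 8.2 also asks for a model-free summary by drug and dose level: "Summary descriptive statistics will include the number of observations, arithmetic and geometric means, standard deviation, coefficient of variation, minimum, and maximum". That list contains no confidence interval. Section 8 leaves the detailed methodology and software to be documented in the PK report. Section 3.2 states: "No formal statistical hypothesis will be tested".

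**The concern.** A drug-plus-subject ANOVA removes differences between subjects before it estimates error. That is what one wants for the within-subject ratio of BIVV001 to Advate. It is not what one wants for a statement about one drug alone, such as the geometric mean half-life or clearance of BIVV001 in patients with severe hemophilia A. How much patients differ from one another is then part of the uncertainty. With subject fixed, the interval treats the subjects in the cohort as the whole population of interest.

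The parameters affected are the secondary endpoints (one-stage assay) and the exploratory endpoints (chromogenic assay), at both doses. With no hypothesis tested, estimates and intervals are the inferential output. The ANOVA is also the only source that the SAP names from which a CI for a single drug's geometric mean could come.

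**Working it through.** **Inputs from the SAP.** Two observations per subject, one per drug; one model per dose level; about 8 and 10 subjects planned, at least 6 and 8 evaluable. There is no figure of the plan's own to reproduce, because it states no variance, precision target or confidence level.

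**Assumptions.** Complete pairs, equal log-scale variance for the two drugs, a 95% level, and a range for rho, the correlation between a subject's log values on the two drugs. With between-subject variance sb² and within-subject variance sw², rho = sb²/(sb² + sw²).

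**Standard errors.**

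- Drug mean, subject fixed: sqrt(MSE/n) on n − 1 df, where MSE is half the variance of the within-subject differences and has expectation sw².
- Drug mean, as an estimate for the patient population: sqrt((sb² + sw²)/n).
- Difference of drug means (log ratio): sqrt(2·MSE/n), whether subject is fixed or random, for complete pairs.

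The fixed-subject interval is therefore about sqrt(1 − rho) times as wide as it should be: 0.84 at rho = 0.3, 0.71 at 0.5 and 0.45 at 0.8.

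**Check of the formulas on one simulated data set** (n = 8, sb = 0.30, sw = 0.15, so rho = 0.09/0.1125 = 0.8):

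| Quantity | Subject fixed | Subject random |
|---|---|---|
| SE of a drug's mean | 0.0336, equal to sqrt(MSE/n) | 0.0805 |
| SE of the difference | 0.0476 | 0.0476 |

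A paired analysis of the same data also gives 0.0476 for the difference.

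**Coverage of the nominal 95% fixed-subject interval for a drug's geometric mean** (100,000 simulated trials per cell):

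| rho | n = 6 | n = 8 | n = 10 |
|---|---|---|---|
| 0 | 95.0% | 94.9% | 95.1% |
| 0.3 | 91.6% | 91.1% | 90.9% |
| 0.5 | 87.2% | 86.1% | 85.5% |
| 0.8 | 69.9% | 67.1% | 66.3% |
| 0.9 | 54.7% | 52.1% | 50.6% |

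Under these assumptions coverage also has a closed form, P(|T| ≤ t·sqrt(1 − rho)), with T on n − 1 df and t its 97.5% point. At n = 8, t = 2.365. For rho = 0.5 the limit is 2.365 × 0.707 = 1.672, which gives 86.2%. For rho = 0.3 and 0.8 the results are 91.2% and 67.5%, in line with the simulation.

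In the same simulations the one-sample t interval on one drug's log values covered 94.8% to 95.1%, and the ratio interval 94.9% to 95.2%.

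**On the reported scale.** Take an assumed total CV of 30% and n = 8. The log SD is sqrt(ln 1.09) = 0.294. The full interval is the geometric mean times or divided by exp(2.365 × 0.294/sqrt(8)) = 1.28. With subject fixed, the factor becomes 1.23, 1.19 and 1.12 at rho = 0.3, 0.5 and 0.8.

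**The case against.** The strongest reply is that the problem is inferred. The SAP does not say that subject is fixed, and with subject random the single-drug interval includes between-subject variance. Nor does it attach a CI to each drug's mean explicitly: CIs are the third item in a list, the model's stated purpose is comparison, and the matching tables in the SAP appendix are titled as comparisons. If only the ratio gets an interval, nothing is wrong. This stands as a limit on the claim, which must be conditional. It does not settle the matter. Factors of an ANOVA, with no random effect mentioned anywhere, ordinarily means fixed effects, and estimated means listed with CIs ordinarily get them. Documenting the method later in the PK report does not change the model that Section 8.2 already fixes.

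Second, the descriptive summary gives n, geometric mean, SD and CV by drug and dose level, so a reader can see how much patients differ. That is true and reduces the harm. It supplies no interval, though, and does not correct one printed beside it.

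Third, the size depends on variances that the SAP does not give. Each drug is given once, so any subject-by-drug interaction falls into the residual; this lowers rho and shrinks the shortfall. Unequal variances would also shift it: the more variable drug fares worse, and the less variable one may lose little or nothing. These points stand.

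**Conclusion.** The point holds as a conditional one. If subject is fixed and CIs are reported for each drug's geometric mean, those CIs are too narrow for the patient population whenever the two drugs' log values are positively correlated within subjects (equal variances assumed). At n = 8 the loss runs from about 4 percentage points of coverage at rho = 0.3 to about 28 at rho = 0.8. The correlations and the 95% level are assumptions.

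A reader might infer more, and the SAP does not support it:

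- *That the intervals are bound to be far too narrow.* No variances are given, and at a modest correlation the loss is modest.
- *That the comparison of BIVV001 with Advate is affected.* The ratio interval rests on within-subject error, as it should.
- *That these intervals drive dose planning or escalation.* Section 3.5 says only that further descriptive interim analyses may support regimen planning. Its escalation conditions concern inhibitor results, completed PK sampling and safety data. No decision in the SAP depends on a single-drug CI.

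**What to change.** In Section 8.2, keep the drug-plus-subject model for the geometric mean ratio and its CI. Add a sentence saying that each drug's geometric mean CI comes from a one-sample t interval on that drug's log-transformed parameter, or from the same model with subject as a random effect. Name which of the two is used, and state the confidence level. If single-drug CIs are not meant to be reported, say that instead.

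The cost is one sentence and a small programming change. The single-drug intervals become wider. The ratio and its CI do not change for complete pairs. The PK analysis set (Section 4.3) admits subjects with adequate samples after either drug, so incomplete pairs are possible. For those, the choice between fixed and random subject can also move the ratio slightly, which is a further reason to state it.

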9. SAFETY ANALYSES

All safety analyses will be conducted using the Safety Analysis Set.

9.1. Adverse Events

Adverse events will be classified using the Medical Dictionary for Regulatory Activities (MedDRA) System Organ Classes and Preferred Terms (Version 20.0 or later). Any AE experienced by the subject from the day of signing the Informed Consent Form until 28 days after BIVV001 administration will be recorded on the eCRF, regardless of the severity of the event or its relationship to study treatment.

A treatment-emergent AE (TEAE) is defined as any adverse event that begins on or after the study treatment (Advate or BIVV001) and within 28 days after BIVV001 administration. AEs with missing start dates will be assumed to be treatment-emergent, unless the stop date is before the dosing date. An AE starting on or after the single dose of study-administered Advate but before the single dose of study-administered BIVV001 will be counted in the Advate Treatment Period. An AE starting on or after the single administration of study-administered BIVV001 and up to the end of study will be counted in the BIVV001 Treatment Period. During the BIVV001 Treatment Period, subjects may resume treatment with their pre-study FVIII product after completing Visit 14 activities. Adverse events that occur during pre-study FVIII product use will be summarized in the BIVV Treatment Period summaries as well as in a separate summary. Adverse events that occur during a major surgical period will be listed separately and will not be included in the AE summary tables.

In general, AEs will be summarized by subject incidence by dose level and overall for the BIVV001 Treatment Period and separately for the Advate Treatment Period. In addition, all AEs will be presented in a data listing by dose level and subject. In this listing, AEs that occur prior to study treatment and AEs that occur during a major surgical period will be flagged.

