9.1.3. Severity of Adverse Events

The severity of AEs will be recorded on the AE form as “Mild”, “Moderate”, or “Severe”. A summary of TEAEs by system organ class, preferred term, dose level, and severity will be presented for the BIVV001 Treatment Period and separately for the Advate Treatment Period.

In addition, all severe adverse events will be presented in data listings by dose level and subject.

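### The TEAE rule works on start date only, so an ongoing event that worsens after BIVV001 can be left out of the BIVV001 tables

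*SAP*

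**What the plan says.** SAP Section 9.1 fixes two rules, and both turn on when an event starts.

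- Treatment emergence: "A treatment-emergent AE (TEAE) is defined as any adverse event that begins on or after the study treatment (Advate or BIVV001". The same sentence ends the window 28 days after BIVV001.
- Period: an event that starts once Advate has been given "but before the single dose of study-administered BIVV001 will be counted in the Advate Treatment Period". For the second drug, "An AE starting on or after the single administration of study-administered BIVV001 and up to the end of study will be counted in the BIVV001" period.

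Collection is wider than the tables. On eCRF entry the section says: "Any AE experienced by the subject from the day of signing the Informed Consent Form until 28 days after BIVV001 administration will be recorded on". An event can therefore already be ongoing when Advate is given. Every AE is also listed: "In this listing, AEs that occur prior to study treatment and AEs that occur during a major surgical period will be flagged".

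The detailed tables use the same periods. Section 9.1.3 states: "A summary of TEAEs by system organ class, preferred term, dose level, and severity will be presented for the BIVV001 Treatment Period", with a matching table for Advate. Sections 9.1.4 (related events) and 9.1.5 (serious events) are built in the same way. Section 9.1.3 does not say which grade is tabulated when severity changes over time.

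Two design facts bear on this. AE occurrence is a primary endpoint (Section 2.2.1). The order is fixed, Advate and then BIVV001, with a short minimum gap: "Washout duration at least 72 hours (3 days) from the Advate dose for the BIVV001 low-dose cohort", and 96 hours for the high-dose cohort (Section 3.1).

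**The concern.** A common definition of a TEAE also takes in events that were present before a dose and became worse after it. This SAP writes out its own rule and has no such clause. In a fixed-sequence study the omission is not neutral between the drugs. The second dose can fall three or four days after the first, and an event that is mild after Advate may still be running when BIVV001 is given. If that event then becomes severe or serious, the start-date rule keeps it under Advate. If it began in screening, the rule keeps it out of the TEAE tables altogether.

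At stake is the tabulated safety profile of a first-in-human product in about 18 subjects, where one event can make up a whole row of a table.

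**Working it through.** **Step 1. Is there a worsening rule anywhere in the SAP?** The places where one could sit are Section 2.2.1 (endpoints), 5.1.1.8 (study day), 5.1.3 (missing data) and 9 to 9.1.6 (adverse events). None deals with an increase in severity or a change to serious, and none says that a worsening opens a new AE record. The rule for missing start dates in Section 9.1 concerns unknown onset, not worsening. The SAP gives no figure on this point, so there is none to reproduce.

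**Step 2. Apply the rule literally.** The result depends on how the worsening is recorded.

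| Event begins | Event worsens | Worsening kept on the original record | Worsening entered as a new AE |
|---|---|---|---|
| Between consent and Advate | After BIVV001 | No TEAE table | BIVV001 tables |
| Between Advate and BIVV001 | After BIVV001 | Advate tables only | Advate tables, then BIVV001 tables |
| After BIVV001 | Later | BIVV001 tables | BIVV001 tables |

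The first two rows are the gap. By this route the BIVV001 tables can lose an event but cannot gain one, because BIVV001 always comes second. In the second row, an event judged related to BIVV001 because it worsened would still be placed in the Advate table of related events.

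**Step 3. Weight of one subject.** The inputs are the planned cohort sizes in Section 3.1: about 8 (low dose), about 10 (high dose) and about 18 in total. The shift is 1/n. The exact one-sided 95% upper limit is 1 − 0.05^(1/n) with no subject affected, and the 0.95 quantile of Beta(2, n − 1) with one.

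| n | Shift 1/n | Upper limit, 0 subjects | Upper limit, 1 subject |
|---|---|---|---|
| 8 | 12.5 points | 31.2% | 47.1% |
| 10 | 10.0 points | 25.9% | 39.4% |
| 18 | 5.6 points | 15.3% | 23.8% |

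Section 9.1.2 counts a subject once at each level of summary. Overall incidence therefore moves by 1/n only if the subject has no other BIVV001-period TEAE. For a single row, such as one preferred term, the condition is that the subject has no other event in that row.

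**Step 4. How likely is at least one such subject?** The SAP gives no rate, so q, the share of subjects with an ongoing event that worsens after BIVV001, is an assumption. The chance of at least one is 1 − (1 − q)^n.

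| n | q = 5% | q = 10% | q = 20% |
|---|---|---|---|
| 8 | 34% | 57% | 83% |
| 10 | 40% | 65% | 89% |
| 18 | 60% | 85% | 98% |

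These figures show scale only. They are not a forecast.

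**The case against.** The strongest reply is that the effect depends on a recording convention that the SAP does not show. If the eCRF instructions or the protocol require a new AE record when an event worsens, that record starts after BIVV001 and Section 9.1 already places it correctly. Such instructions are often kept outside the SAP, and the protocol is not at hand. This stands, and it is why the point is conditional. It does not remove the need for a sentence in the SAP: Section 9.1 sets out the emergence and period rules in full and does not refer elsewhere for worsening.

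The second reply is that nothing is hidden. All AEs are listed, and Sections 9.1.3 to 9.1.6 add listings of severe, related and serious events and of withdrawals. About 18 subjects can be read one by one, the DSMC sees listings as well as summaries (Section 3.5), and no hypothesis is tested (Section 3.2). This also stands, and it limits the harm to tabulation. But Section 9.1 summarizes AEs by subject incidence per period, and a listing does not correct a table that others will cite.

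The third reply is that causality is assessed separately, with a category for relation to BIVV001 (Section 9.1.4). That helps in the listing, but the summary of related events is still split by period.

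A reader might go further and infer that BIVV001 toxicity is undercounted, that worsened events disappear, that events will overlap the second dose, or that a severe grade is bound to appear under Advate. The document supports none of these as a certainty. The listings keep the events, 72 and 96 hours are minimum gaps with no rate of ongoing events given, and Section 9.1.3 does not say that a single record carries the worst grade.

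**Conclusion.** The point holds in conditional form and should be corrected before tabulation. Section 9.1 identifies TEAEs and assigns their period by start date alone, with no provision for worsening. Unless a worsening is recorded as a new AE with its own start date, the BIVV001 summaries of TEAEs, severity, related events and serious events can be understated, and an event made worse by BIVV001 can be tabulated under Advate.

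The size is 12.5, 10 or 5.6 percentage points of overall incidence for each subject whose only BIVV001-period event is such a worsening. This rests on the planned cohort sizes. How many subjects would be affected cannot be worked out from the document, and the number may be zero. Data collection and the listings are not affected.

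**What to change.** In SAP Section 9.1:

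- Define a TEAE as an AE that begins, increases in severity or becomes serious on or after a dose and no later than 28 days after BIVV001.
- Count a worsened event in the period in which it worsened, at the worsened grade. Keep an event with onset between the doses in the Advate period as well, at the grade it had before BIVV001. Apply this to the severity, related and serious tables too.
- State how worsening is recorded. If the eCRF opens a new record, say so and use that record's start date. If no date of worsening is captured, identify these events from the listings before the tables are produced, and document the decisions.

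The cost is a few sentences and minor programming where the worsening is dated. Where it is not, wording alone will not assign the event, and a review of the listings for about 18 subjects is needed. The downside is that one event may appear in both period tables and TEAE counts may rise slightly; a table footnote can explain this.

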9.1.1. Overall Summary of Treatment-Emergent Adverse Events

An overall summary of treatment-emergent adverse events (TEAEs) will be provided which tabulates the number and percentage of subjects who experience a TEAE, related TEAE, treatment-emergent SAE, related treatment-emergent SAE, and the number and percentage of subjects who withdrew from the study due to an AE. The overall summary will be provided by dose level for the BIVV001 Treatment Period and separately by dose level for the Advate Treatment Period.

